4.5.4 Vital Signs

Vital signs will include measurements of respiratory rate, pulse rate, peripheral oxygen saturation, systolic and diastolic blood pressures, and body temperature. Body temperature should be measured using the same methodology throughout the study.

For patients requiring supplemental oxygen, the oxygen flow rate (L/min) and/or fraction of inspired oxygen (FiO_2) should be recorded.

All of the vital sign parameters should be recorded *together* four times per day for the duration of the hospitalization throughout the treatment period (Day 1/Visit 1 to Day 10). It is recommended that the collection timepoints for vital signs and assessments (specific to NEWS2, Section 4.5.4) are spread throughout the study day to reflect the patient's condition over the entire study day, where possible. Following hospital discharge during the treatment period (Day 1 to Day 10) these parameters should be recorded once at each return visit to the clinic. Patients who remain hospitalized during the follow-up period (Day 11+) require daily collection of vital signs for the purpose of the study. During the follow-up period in patients who have been discharged, vital sign measurements and temperature are to be recorded at the investigators' discretion (e.g., if symptoms and signs persist during follow-up). Vital sign measurements may be performed by an MN professional.

4.5.5 Assessments Specific to National Early Warning Score 2

In addition to the vital measurements, the patient's consciousness level and the presence or absence of respiratory support must be recorded. The NEWS2 parameter for respiratory support is the selection of either air or oxygen –“oxygen” can include other forms of ventilation to maintain oxygen saturation (see [Appendix 3](#)).

These should be recorded at the same time points as the vital sign measurements (see Section 4.5.4 and [Appendix 1](#)).

4.5.6 National Early Warning Score 2

The NEWS2 should be calculated by the site at screening only based upon vital sign values and assessments related to National Early Warning Score 2 (see Section 4.5.5) recorded during the patient assessment. Should these assessments be conducted more than once during the screening period (per site patient care), all data collected closest to but before randomization should be used for the NEWS2 score calculation and assessment of patient eligibility. See [Appendix 3](#) for calculation instructions.

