6.4.1 Primary Efficacy Endpoint

The primary efficacy objective for this study is to evaluate the efficacy of baloxavir marboxil plus a SOC NAI, compared with matching placebo plus SOC NAI on the basis of the following endpoint:

- TTCI (defined as time to hospital discharge or time to NEWS2 of ≤ 2 and maintained for 24 hours, whichever comes first)

The median TTCI will be compared between the baloxavir marboxil plus SOC NAI and matching placebo plus SOC NAI arms using the stratified log-rank test within three regions (*i.e.*, North America, EMEA, ROW), NEWS2 (≤ 7 , > 7), and time from symptom onset to study treatment (≤ 48 hours, > 48 hours) included as the stratification factors. The Kaplan-Meier plot, median time to response, 95% CIs, and p-values will be presented.

The log-rank test requires the assumption of proportional hazards to be met. The proportional hazards assumption will be tested graphically using the log cumulative hazard plot by treatment group. The plots for each treatment group will be parallel if the

proportional hazard assumption holds. *Using a Cox model, the slope of a linear regression will also be tested and a plot of scaled Schoenfeld residuals against the Kaplan-Meier estimator investigated.*

Should the proportional hazards assumption be violated, the Gehan-Wilcoxon test will be used to analyze the data *as the logrank test can be under powered in this situation.* All investigations will be detailed in the statistical section of the CSR.

The estimand is the median change in TTCI. This absolute measure will be assessed over the duration of the study (35 days). Intercurrent events are those that occur after treatment initiation and either preclude observation of the variable or affect its interpretation. Intercurrent events will be accounted for through censoring rules. Patients who are lost to follow-up, who do not have a clinical response event, who die or discontinue for any reason prior to achieving a clinical response event will be censored at their last contact date or date of death, whichever is applicable. No dose reductions or treatment cross-overs are anticipated.

As specified in Section 6.4, the primary efficacy analysis population will be the modified-ITTI population, which consists of all patients who were randomized to treatment, received a dose of study drug, and were RT-PCR positive for influenza *at any timepoint.*

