The TTCI will be compared between the baloxavir marboxil plus SOC NAI and matching placebo plus SOC NAI arms using the stratified log-rank test within three regions (i.e. North America, EMEA, ROW), NEWS2 score at baseline (≤ 7 , > 7), and time from symptom onset to study treatment (≤ 48 hours, > 48 hours) included as the stratification factors. The Kaplan Meier plot, median time to response, 95% CIs, and p-values will be presented.

The log-rank test is most appropriate when the assumption of proportional hazards is met. The proportional hazards assumption will be tested graphically using the log cumulative hazard plot by treatment group. The plots for each treatment group will be parallel if the proportional hazard assumption holds. Should the proportional hazards assumption be violated, the Gehan Wilcoxon test will be used to analyze the data.

The estimand is the difference in distributions between baloxavir marboxil plus SOC NAI and matching placebo plus SOC NAI arms in the mTTi for the TTCI using appropriate method, as described above. This absolute measure will be assessed over the duration of the study (35 days). The median TTCI for each treatment group and difference between treatment groups will be presented. Intercurrent events are those that occur after treatment initiation and either preclude observation of the variable or affect its interpretation. Intercurrent events, such as patients who are lost to follow-up, die or discontinue for any reason prior to achieving a clinical improvement or do not have a clinical improvement event, will be accounted for through censoring rules, as described in [Table 4](#) below.

Table 4 TTCI and Censoring

Event	Censor	Date and Time
Clinical improvement (based on NEWS2 \leq 2 for 24 hours)	No	vital signs assessment where NEWS2 \leq 2 at start of 24 hour period
Clinical improvement (based on NEWS2 \leq 2 prior to discharge)	No	first vital signs assessment where NEWS2 \leq 2 prior to discharge
Clinical improvement (based on hospital discharge)		
- hospital discharge and hospital re-admission within 24 hours) and discontinue study on same day	Yes	hospital discharge
- hospital discharge and hospital re-admission within 24 hours) and continue study	Yes	hospital discharge
- hospital discharge against medical advice (i.e. self-discharge)	Yes	hospital discharge
- all other hospital discharge	No	hospital discharge
Death prior to achieving a clinical improvement	Yes	last vital signs assessment prior to death

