Event	Censor	Date and Time
Clinical Response (based on vital signs assessments)	No	first vital signs assessment where 4 out of 5 criteria initially met and subsequently maintained for 24 hours period
Clinical Response (based on vital signs criteria met prior to discharge)	No	first vital signs assessment where 4 out of 5 criteria initially met and maintained prior to discharge
Clinical Response (based on hospital discharge)		
- hospital discharge to another hospital (i.e. hospital admission within 24 hours) and discontinue study on same day	Yes	hospital discharge
- hospital discharge to another hospital (i.e. hospital admission within 24 hours) and continue study	Yes	hospital discharge
- hospital discharge against medical advice	Yes	hospital discharge
- all other hospital discharge	No	hospital discharge
Death prior to achieving a clinical response	Yes	last vital signs assessment prior to death
Discontinuation for any reason prior to achieving a clinical response	Yes	last vital signs assessment prior to discontinuation
Lost to follow-up	Yes	last vital signs assessment
No clinical response	Yes	last vital signs assessment

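### Patients back in hospital within 24 hours who stay in the study are censored at the failed discharge, although their follow-up continues

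*SAP*

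**What the plan says.** Protocol 6.4.1 defines the primary endpoint as "TTCI (defined as time to hospital discharge or time to NEWS2 of ≤ 2 and maintained for 24 hours, whichever comes first". It has no exception for readmission, transfer or self-discharge. Patients without an event are censored at last contact, or at death.

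SAP 4.5.1, Table 4, divides discharge into four rows:

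- "hospital discharge and hospital re-admission within 24 hours) and discontinue study on same day": censored at discharge.
- "hospital discharge and hospital re-admission within 24 hours) and continue study": censored at discharge.
- "hospital discharge against medical advice (i.e. self-discharge": censored at discharge.
- "all other hospital discharge": an event at discharge.

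Table 7 (time to clinical response) and Table 10 (time to hospital discharge) word the second row as "hospital discharge to another hospital (i.e. hospital admission within 24 hours) and continue study", again censored at discharge. The rule therefore touches the primary endpoint, a key secondary endpoint and another secondary endpoint.

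On data collection, protocol 4.5.4 requires vital signs "four times per day for the duration of the hospitalization throughout the treatment period (Day 1/Visit 1 to Day 10", and then: "Patients who remain hospitalized during the follow-up period (Day 11+) require daily collection of vital signs for the purpose of the study". The schedule of activities asks for Visits 1 to 7 from everyone, in hospital or not.

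SAP 3.3 lists two changes from the protocol, the interim futility statistic and the definition of clinical response. The discharge rows are not among them.

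**The concern.** By refusing to count the failed discharge as an event, the SAP accepts that the patient has not improved. A patient who has not improved and is still in the study would ordinarily stay at risk. Table 4 instead removes that patient at the moment of the failed discharge and ignores what follows. The log-rank test and the Kaplan-Meier estimate then treat the patient as having the same future chance of improvement as those still at risk. Someone back in hospital within a day is likely to do worse than that.

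If the two arms have such patients at similar rates, both curves look slightly too good and the comparison changes little. If the rates differ, the estimated treatment effect is biased towards the arm with more failed discharges.

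**Working it through.** **1. The rules side by side.** There are three candidate treatments of a patient who is discharged, returns within 24 hours and continues the study.

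| Source | Treatment |
|---|---|
| Protocol 6.4.1, read literally | Event at the discharge |
| Protocol 6.4.1, if that discharge is not accepted as an event | At risk until a later event; otherwise censored at last contact |
| SAP Table 4 | Censored at the discharge |

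The SAP rule matches neither reading of the protocol. It also differs from Table 4's own row for patients who never improve, which censors at the last vital signs assessment.

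The affected group is limited. A patient who already held NEWS2 at 2 or less for 24 hours has an event before discharge. A patient who reached 2 or less shortly before discharge and then returned fits both an event row and a censored row, and no precedence is given.

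**2. The plan's own figure.** Inputs from SAP 2.4 and 2.5.1: 366 randomised, 75% RT-PCR positive, 4% dropout, 176:88, medians 94 and 63 h (94 − 31), 840 h follow-up, two-sided 5%, futility bound p about 0.077 at 65% of events.

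- 366 × 0.75 × 0.96 = 263.5, against 264 stated.
- Hazard ratio for improvement under exponential times: 94/63 = 1.492. Expected events: about 263.8.
- Drift: ln(1.492) × √(263.8 × 2/9) = 3.064. Fixed-design power: Φ(3.064 − 1.960) = 86.5%.
- With the futility bound (taking 0.077 as a one-sided p, which is how it reproduces): 80.3%.

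The stated 80% power therefore reproduces, with almost no margin.

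**3. Events lost.** Suppose a fraction q of patients is censored at a failed discharge and the hazard ratio is unchanged. The documents give no q, so a range is shown.

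| q | Events | Fixed-design power | Power with futility bound |
|---|---|---|---|
| 0 | 263.8 | 86.5% | 80.3% |
| 1% | 261.2 | 86.2% | 79.9% |
| 2% | 258.5 | 85.8% | 79.5% |
| 5% | 250.6 | 84.8% | 78.2% |
| 10% | 237.4 | 82.8% | 76.0% |

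**4. Informative censoring.** Simulation with 4,000 trials per scenario, 176:88, exponential times, failed discharge uniform on 24-96 h, later time to improvement exponential with twice the mean, log-rank at two-sided 5%, no interim. All rates are assumed. Each row gives the chance of p<0.05.

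| Affected, baloxavir / placebo | Medians (h) | SAP rule | Followed to outcome |
|---|---|---|---|
| 5% / 5% | 75 / 94 | 38% | 37% |
| 8% / 2% | 75 / 94 | 30% | 17-18% |
| 8% / 2%, only patients not yet improved can be affected | 75 / 94 | 39% | 30% |
| 2% / 8% | 75 / 94 | 45-46% | 59% |
| 5% / 5% | 94 / 94 (no effect) | 5.0% | 5.6% |

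At 3-5% in both arms the control median is understated by about 2-3 h and power moves by 1-2 points. In a separate set of 6,000 runs with no treatment effect and remaining recovery time doubled, the SAP rule rejected in 5.5% (10% baloxavir, 5% placebo) and 5.9% (5%, 10%). Following patients to outcome gave 5.3% and 5.5%.

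**The case against.** **The SAP rule is stricter than the protocol.** Read literally, the protocol would credit a failed discharge as improvement, and the SAP withholds that credit. This is a fair point in the SAP's favour. It supports not counting an event, but it does not support ending follow-up.

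**The outcome may not be observed.** The frequent vital signs apply during hospitalisation. After discharge in the treatment period there is one reading per return visit, which cannot show a score held for 24 hours. Nothing says that a non-study hospital will supply NEWS2 components. This stands, and the fix has to allow for it.

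**An existing sensitivity analysis may cover it.** SAP 4.5.1.1 censors at 35 days patients without a response event. Whether that includes readmitted patients is unclear. If it does, it still ignores any later improvement that was recorded.

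**The effect is small.** At equal rates this is correct.

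A reader might also infer that every other discharge counts as success, including discharge to palliative care. The documents do not support stating it that way. Self-discharge and readmission with same-day discontinuation are censored, and neither document mentions palliative care, hospice or a discharge-destination field. Holding such patients at risk to Day 35 would also be inconsistent with censoring in-hospital deaths at the last vital signs assessment. It would cut simulated power from about 85% to about 69% if 2% of patients in both arms were affected.

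**Conclusion.** The point holds for patients who return to hospital or are transferred within 24 hours and continue the study. Tables 4, 7 and 10 end their follow-up at a discharge that the SAP itself does not accept as improvement. The rule is not in the protocol, is not declared in SAP 3.3, and no sensitivity analysis clearly tests it.

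The size depends on rates that the documents do not give. At assumed equal rates of 3-5% it is about 1-2 points of power and 2-3 h on the control median, with type I error close to 5%. With unequal rates the bias can flatter baloxavir or hide a benefit.

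A reader might take the 30% against 17-18% contrast as the expected distortion. It is not: it needs an assumed fourfold imbalance against baloxavir in a double-blind trial. It shrinks to 39% against 30% when only patients not yet improved can be affected, and it changes direction when the imbalance is reversed. The case for change is that the remedy is cheap and removes an avoidable assumption, not that the primary result is in serious doubt.

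**What to change.** 1. In the continue-study rows of Tables 4, 7 and 10, treat readmission or transfer within 24 hours as continued hospitalisation. Keep the patient at risk until the NEWS2 criterion (Table 4) or the clinical response criteria (Table 7) are held for 24 hours, or until final discharge. For Table 10, use final discharge only. If none is observed, censor at the last available assessment.
2. Use the same wording in all three tables, so that it is clear whether Table 4 covers transfer as well as readmission.
3. State which row applies when NEWS2 reached 2 or less just before such a discharge.
4. List the change in SAP 3.3 and keep the current rule as a sensitivity analysis. Report the number of affected patients by arm.

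The cost is SAP wording and derivation code. Medians will be slightly longer, and the rule relies on assessments and discharge times from the receiving hospital. Where those are missing, the patient is censored at the last assessment available.

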4.5.1.1 Sensitivity Analysis

The following sensitivity analyses will be conducted:

1. to examine the effect of subjects who discontinue for any reason prior to achieving a clinical response event
 - patients who are lost to follow-up or who do not have a clinical response event will be censored at 35 days.
 - any imbalance in demographics, disease characteristics and influenza history between treatment arms will be assessed in relation to reasons for discontinuation to identify any confounding factors. Identified confounding factors will be adjusted for in a sensitivity analysis.
 - considering death as a competitive event, using a competing risk model will be conducted if there are a sufficient number of deaths (~10%) or an imbalance between groups in deaths and reason attributed.
2. to examine the effect of artificial support, defined as receiving non-invasive mechanical ventilation, mechanical ventilation, Extracorporeal membrane oxygenation (ECMO) and/or inotropic support
 - patients who met the NEWS2 criteria (≤ 2 for 24 hours) and received artificial support during this time period will be censored at the vital signs assessment where $\text{NEWS2} \leq 2$ at start of 24 hour period.

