2.4 DETERMINATION OF SAMPLE SIZE

The required sample size of the modified intent-to-treat infected (mITTI) population is 264 patients (176 patients in the baloxavir marboxil group and 88 in the placebo group). It is assumed that the reverse transcriptase polymerase chain reaction (RT-PCR)–positive rate (tested in a central laboratory) will be 75% of the randomized population; hence, approximately 366 patients will be randomized to ensure an adequate number of patients in the mITTI population and to allow for a 4% dropout rate. The total number of randomized patients may change based on the percentage of patients who are RT-PCR positive during the study.

The total mITTI sample size of 264 patients provides at least 80% power using the log-rank Chi-Square test to detect a 31-hour difference in the time to clinical improvement (TTCl) between treatment groups under the following assumptions: median TTCl in the placebo plus NAI group is 94 hours, 840 hours follow-up (35 days), using an alpha of 5%, and the minimal detectable difference is 23 hours. The TTCl in the placebo plus NAI group of 94 hours was selected after consideration of the response rates observed in a blinded review of TTCl including data from 127 patients.

The study power is calculated based on the primary endpoint incorporating a group sequential design (GSD) using a beta spending function with non-binding rule, to allow for one futility interim, without increasing the overall experiment-wise error rate.

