4.5.4 Subgroup Analyses

The TICI will be compared between the baloxavir marboxil plus SOC NAI and matching placebo plus SOC NAI arms for the following subgroups:

- region
 - North America (United States, Canada);
 - Europe, Middle East, and Africa [EMEA] (Belgium, Bulgaria, Czech Republic, Estonia, France, Germany, Hungary, Israel, Netherlands, Romania, Serbia, Spain, Sweden, Turkey, Ukraine);
 - Rest of world [ROW] (Mexico, Japan, South Korea, Brazil, Argentina, Peru, Australia, New Zealand, Hong Kong, Singapore, China)
- baseline age (<65, ≥65 years)
- baseline age (<80, ≥80 years)
- baseline NEWS2 score (≤7, >7)
- time from symptom onset to study treatment (≤48 hours, >48 hours)
- ICU or mechanical (invasive/non-invasive mechanical or ECMO) intervention at baseline or any point during the study prior to clinical improvement (Yes, No)
- Patients who received anti-influenza drug within 48 hours prior to screening (including Oseltamivir, Zanamivir, Peramivir, Laninamivir, Arbidol, Favipiravir, Amantadine, Rimantadine) (Yes, No)
- On-treatment NAI (Oseltamivir, Zanamivir, Peramivir)
- Immunocompromised patients (Yes, No) – see [Appendix 6](#)
- Patients with ongoing comorbidities at baseline
 - Respiratory comorbidities:
 - Pneumonia (Yes, No). Including any event preferred term with “pneumonia”.
 - Respiratory thoracic and mediastinal disorders System Organ Class and/or pneumonia (Yes/ No)
 - Respiratory influenza complications that required or extended hospitalization, defined as required ventilation or supplemental oxygen and/or complications of ‘respiratory’ class as assessed by the investigator
 - Cardiac comorbidities
 - Cardiac disorders System Organ Class

- Cardiac influenza complications that required or extended hospitalization, defined as complications of ‘Cardiac’ class as assessed by the investigator
- Patients contracting nosocomial influenza (e.g. prolonged hospitalization)
- influenza subtype (A, B) at baseline– will be conducted if >10% patients in B
- virus subtype (H1, H3) at baseline
- presence of co-respiratory infection at baseline (identified via the non-influenza respiratory bacterial and virus co-infection panel) (Yes, No)
- high and low baseline viral titre e.g. 2 groups split at the median
- high and low viral titre AUC e.g. 2 groups split at the median

Subgroups will be analyzed descriptively. The median TTCl for each subgroup and a 95% CI will be presented.

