Appendix 4 National Early Warning Score 2 (NEWS2)

Physiological parameter	Score						
	3	2	1	0	1	2	3
Respiration rate (per minute)	≤8		9–11	12–20		21–24	≥25
SpO ₂ Scale 1 (%)	≤91	92–93	94–95	≥96			
SpO ₂ Scale 2 (%)	≤83	84–85	86–87	88–92 ≥93 on air	93–94 on oxygen	95–96 on oxygen	≥97 on oxygen
Air or oxygen?		Oxygen		Air			
Systolic blood pressure (mmHg)	≤90	91–100	101–110	111–219			≥220
Pulse (per minute)	≤40		41–50	51–90	91–110	111–130	≥131
Consciousness				Alert			CVPU
Temperature (°C)	≤35.0		35.1–36.0	36.1–38.0	38.1–39.0	≥39.1	

Reference

Royal College of Physicians. National early warning score (NEWS) 2 Standardizing the assessment of acute-illness severity in the NHS. London: RCP, 2017.

At screening, the NEWS2 should be calculated based upon vital sign values recorded during the patient assessment. *Should these vital signs assessments be recorded more than once during the screening period (per site patient care) all data collected closest to but before randomization should be used for the NEWS2 score calculation and assessment of patient eligibility.*

The oxygen saturation should be scored according to either the SpO₂ Scale 1 or 2 presented in the table above. The SpO₂ Scale 2 is for patients with a target oxygen saturation requirement of 88%–92% (e.g., in patients with hypercapnic respiratory failure related to advanced lung diseases, such as chronic obstructive pulmonary disease [COPD]). This should only be used in patients confirmed to have hypercapnic respiratory failure by blood gas analysis on either a prior or their current hospital admission.

The decision to use the SpO₂ Scale 2 should be made by the treating physician and should be recorded in the eCRF. In all other circumstances, the SpO₂ Scale 1 should be used.

For physiological parameter “Air or Oxygen?”: Any patients requiring the use of oxygen or other forms of ventilation to maintain oxygen saturations and support respiration should be assigned a score of 2.

The consciousness level should be recorded according to the best clinical condition of the patient during the assessment. Patients who are assessed as “Alert” (A) should be assigned a score of 0. Patients assessed as “New Confusion” (C), “Responsive to Voice” (V), “Responsive to Pain” (P), or “Unconscious” should be assigned a score of 3.

Scores should be assigned for respiratory rate, systolic blood pressure, pulse, and temperature according to the table above.

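### The artificial-support check on TTCI turns an event into a censoring at the same time point, so it can under-correct when supported patients improve more slowly and are unevenly split between arms

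*SAP*

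**What the plan says.** SAP 4.5.1.1, item 2, defines artificial support as "receiving non-invasive mechanical ventilation, mechanical ventilation, Extracorporeal membrane oxygenation (ECMO) and/or inotropic support". A patient who reached NEWS2 ≤2 for 24 hours and "received artificial support during this time period will be censored at the vital signs assessment" at which that period began. In SAP Table 4 that same assessment is the event time for the primary analysis. Follow-up after it is not used.

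Item 1 of the same section treats other patients without an event differently: "patients who are lost to follow-up or who do not have a clinical response event will be censored at 35 days".

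On scoring, SAP Appendix 4 says that patients needing "oxygen or other forms of ventilation to maintain oxygen saturations and support respiration should be assigned a score of 2". Inotropes are not a NEWS2 component. A patient who is not alert scores 3 for consciousness.

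On data, Protocol 4.5.4 has vital signs recorded four times a day in hospital to Day 10, and after that: "Patients who remain hospitalized during the follow-up period (Day 11+) require daily collection of vital signs". SAP 4.5.3 takes ventilation status from the vital signs log. SAP 4.5.2.3 needs inotrope timing for its blood-pressure criterion. Discharge time is already part of TTCI.

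The protocol does not specify this sensitivity analysis.

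**The concern.** A patient whose score falls to 2 while on ventilation, ECMO or inotropes has not improved unaided, and is still being observed. Censoring at that moment lets the other patients still at risk stand in for this patient's later course. It assumes that someone on support will reach unaided improvement as fast as someone without it, which is close to the question being asked. The plan itself treats ventilated patients as worse off: SAP 4.5.3 counts mechanical ventilation as clinical failure.

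The check exists for the case where supported scores contribute unequally to the two arms. In that case, slower patients are removed from the arm that has more of them, part of the artefact stays, and a reader could take the result as reassurance that support does not matter.

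**Working it through.** **1. One patient under three rules.** Let t1 be the start of a 24-hour NEWS2 ≤2 period reached on support, and t2 > t1 the start of the first such period without support, or a qualifying discharge.

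- Primary analysis (Table 4): event at t1.
- Item 2: censored at t1.
- Kept at risk: event at t2, otherwise censored under Table 4.

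Item 2 changes only the event indicator. The interval from t1 to t2 is observed but not used.

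**2. Who can be flagged.** NEWS2 has seven components. A ventilated patient scores 2 for respiratory support, so the other six must all be 0: 2 + 0 = 2. A ventilated patient who is not alert scores at least 2 + 3 = 5 and cannot qualify. An inotrope recipient on room air gets no points for support and can have up to 2 points elsewhere, but must also be alert. The affected group is therefore alert ventilated patients with every other component at zero, plus inotrope recipients with a total of 2 or less. The documents give no count.

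**3. The plan's own figures, as the base for a simulation.** From SAP 2.4: medians 94 and 94 − 31 = 63 h, allocation 2:1, two-sided 5% alpha, 80% power, 840 h follow-up.

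- Ratio 63/94 = 0.670, with ln = −0.400.
- Fixed-design events (Schoenfeld): (1.960 + 0.842)² / [(2/3)(1/3)(0.400)²] = 221.
- With the non-binding Pocock-type futility look at 65% of events: 262 events. About 264 are expected from 264 patients.
- Randomized: 366 × 0.75 × 0.96 = 263.5.

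The stated 264 is reproduced, and nothing below changes it.

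**4. Simulation of the rule.** These assumptions are not in the documents:

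- 10, 20 or 30% of patients need support.
- Unaided improvement has median 94 h without support and 4 × 94 = 376 h with it.
- A supported NEWS2 ≤2 has median 48 h and is possible in a set share of supported patients.

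The flagged share is (share needing support) × (share able) × 376/(376 + 48). For 20% and 80% this is 0.20 × 0.80 × 0.887 = 14.2%. Hazard ratios (HR) are improvement rates, active over placebo, from 600,000 patients. Rejection rates are from 2,000 trials of 176:88 with an unstratified log-rank test. The Monte Carlo standard error at 2.5% is √(0.025 × 0.975/2000) = 0.35 points.

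| Scenario | Flagged %, active / placebo | HR primary | HR item 2 | HR kept at risk | % significant for active: primary / item 2 / kept |
|---|---|---|---|---|---|
| No effect, able 80% vs 20%, 10% supported | 7.1 / 1.8 | 1.150 | 1.093 | 1.001 | 17.3 / 9.0 / 2.1 |
| Same, 20% supported | 14.2 / 3.6 | 1.288 | 1.162 | 1.000 | 49.0 / 18.8 / 2.5 |
| Same, 30% supported | 21.2 / 5.3 | 1.416 | 1.211 | 0.999 | 74.7 / 27.6 / 2.1 |
| No effect, able 20% vs 80%, 20% supported | 3.6 / 14.3 | 0.778 | 0.867 | 0.999 | 0.0 / 0.1 / 2.5 |
| No effect, able 60% in both, 20% supported | 10.7 / 10.5 | 0.994 | 0.992 | 0.991 | 2.0 / 1.7 / 2.1 |
| No effect, able 80% vs 20%, 20% supported, same later rate | 10.5 / 2.7 | 1.087 | 1.001 | 1.001 | 8.8 / 1.7 / 2.1 |
| Planned effect, able 60% in both, 10% supported | 5.1 / 5.3 | 1.409 | 1.424 | 1.387 | 74.3 / 74.2 / 69.4 |
| Same, 20% supported | 10.1 / 10.8 | 1.357 | 1.388 | 1.356 | 62.8 / 63.1 / 62.7 |
| Same, 30% supported | 15.1 / 16.0 | 1.328 | 1.372 | 1.352 | 58.2 / 59.2 / 60.1 |

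**5. How much of the artefact item 2 removes** (first three rows):

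- Log HR scale, 1 − ln(HR item 2)/ln(HR primary): 1 − 0.0889/0.1398 = 36%; 1 − 0.1501/0.2531 = 41%; 1 − 0.1914/0.3478 = 45%.
- Difference in medians: from 10.6 to 3.1 h (71% removed), 22.6 to 7.6 h (66%), 34.0 to 11.5 h (66%).

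The fourth row shows the bias reversing when placebo has more flagged patients. The fifth and sixth show no bias under balance or under a common later rate. In the last three, item 2 and the kept-at-risk rule differ by at most 1.424/1.387 = 1.027.

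**The case against.** The strongest defence is that item 2 does what it announces: supported scores stop counting as events, and the estimate moves the right way. It is valid if supported patients later improve at the common rate, and harmless under no effect if they are balanced. Censoring is also how this plan handles intercurrent events generally. All of that is correct, so a reader who infers that the check cannot test anything about support goes too far.

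A reader might also infer that the bias favours baloxavir. The documents do not support that. They do not say which arm would have more flagged patients, and the simulated bias changes sign with the imbalance. The 80% versus 20% split and the fourfold slowing were chosen to show the mechanism and are not forecasts. Nor do the documents give the time from a supported score to unaided improvement, so no number of days lost per patient can be stated.

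Other analyses would show a support artefact in part. Time to clinical response generally requires saturation without supplemental oxygen and excludes blood pressure readings taken soon after inotropes. The Day 7 ordinal scale separates ventilated patients. Ventilation incidence and duration and time to discharge are analysed. TTCI is summarised by ICU or ventilatory "intervention at baseline or any point during the study prior to clinical improvement (Yes, No"). These limit the risk of misreading, but none repeats the TTCI comparison with supported scores removed. The subgroup is descriptive and depends on what happens after baseline. The defence reduces the size of the point; it does not make the censoring assumption plausible.

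**Conclusion.** The point holds in a limited form. Item 2 measures the effect of support only under a non-informative censoring assumption that is implausible for patients still on ventilation, ECMO or inotropes. Two conditions together make it under-correct: flagged patients are slower to improve, and they are unevenly split between arms. The residual bias then favours the arm with more of them. With strong assumed values of both, 55 to 64% of the log hazard ratio artefact remained; with balance, the effect was small.

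The group is narrow and its size is unknown, so no effect on this trial's result can be predicted. The primary test, its alpha, its power and the sample size do not depend on this analysis. It is a free improvement to one sensitivity analysis, and a reader should not take it as a reason to doubt the primary result.

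**What to change.** Replace the rule in SAP 4.5.1.1, item 2, with wording such as:

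*In this sensitivity analysis, a NEWS2 ≤2 period during which the patient received artificial support is not an event. The patient remains at risk until the start of the first 24-hour NEWS2 ≤2 period without such support, or a hospital discharge that Table 4 counts as an event, whichever is first. Otherwise the patient is censored under Table 4's rules for death, discontinuation, loss to follow-up, self-discharge, re-admission within 24 hours and no improvement. The number of patients with a supported NEWS2 ≤2 period is reported by arm.*

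This follows the logic of time to clinical response, where a criterion unmet because of support simply leaves the patient at risk. Two shortcuts should be avoided. Ending follow-up at any discharge would count self-discharges and early re-admissions that Table 4 censors. Censoring all flagged patients at Day 35 as never improved over-corrects: in the first three scenarios it gave HR 0.918, 0.857 and 0.796 where the true value was 1.

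Cost: one SAP sentence and one changed derivation. Vital signs, ventilation status, inotrope timing and discharge are already collected.
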